### **Exclusion criteria**

Stridor or marked laryngeal or tracheal stenosis, vocal cords polyps, emergency surgery, high aspiration risk, decompensated cardiac and pulmonary disease, very poor dentition and patient refusal were criteria of exclusion from the study. We've also decided to reject from the study patients who exhibit a Cormack-Lehane grade 1 glottis view when conventional laryngoscopy is performed. In case of difficult mask ventilation causing marked desaturation, requiring prompt action to secure the airway, we will take the first chance to secure the airway considering potentially unsafe the use of the experimental RTL. The

investigator underwent a training period before starting the study, consisting in ten direct laryngoscopies with the RTL under an ENT specialist guidance to get used to manoeuvring the RTL and acquire a reasonable level of skill in using it.

A pre-anaesthetic exam was performed with careful assessment of the airway. Patients with features predictive for difficult intubation gathering at least 4 points on the SARI score and with no known airway pathology were included in group 1. Patients from the group 2, with obstructing airway pathology had a perioperative endoscopic examination of the airway with a flexible rhino-laryngoscope which is meant to evaluate the distorted anatomy and exclude glottic or subglottic stenosis which could contraindicate blind intubation over an intubating tube introducer (gum elastic bougie).

Premedication consisted of 1 or 2 mg of Midazolam given intravenously 15 minutes before the intervention, in the preoperative room. Standard hemodynamic and respiratory monitoring were applied: ECG, non-invasive arterial blood pressure, oxygen saturation, respiratory frequency, end-tidal CO2. Difficult airway kit was prepared. The RTL was in position with the light source attached. Patients were pre oxygenated for 5 minutes and induction of anesthesia with propofol- succinylcholine and fentanyl was performed. After 1 minute of mask ventilation, we noted the oxygen saturation on the pulse oximeter, classical laryngoscopy was performed with a McIntosh curved blade laryngoscope, and CormackLehane glottis visualization was registered- possible values: 1,2,3,3.5,4.

The RTL intubation starts with the head in extension and in sniffing position, using a retromolar approach, with teeth protection. The approaching side was chosen based on patient pathology and it could be changed during the procedure if the investigator considered so. We used a 1.2-2.2 cm wide and 15-30 cm long tube depending on patient preoperative assessment and pathology. During advancement of the RTL, the investigator is careful to apply the minimum of pressure so the oro-pharyngeal tissue and dentition should not be injured. The RTL was advanced slowly until it reached the epiglottis, then the

epiglottis was lifted, and the vocal cords visualised. The thyroid cartilage was a land point when advancing the RTL, keeping the RTL on its direction and holding pressure on it and thus adjusting the larynx position so the epiglottis and glottis should be easier to visualise with the RTL. After a proper alignment between the RTL and the glottis was achieved, the bougie was introduced through the RTL into the glottis, the RTL extracted, and the standard cuffed intubating tube with lubricated tip was placed in the trachea gently, over the bougie. Secretions were aspirated through the RTL as needed. If the glottis is visualised during the RTL advancement, it will be withdrawing slowly, and the larynx will be manipulated with the left hand from the thyroid cartilage until the glottis comes into sight. A second attempt will be started advancing slower, heading to the thyroid cartilage while looking for epiglottis. Once epiglottis is lifted the RTL must be directed as anteriorly as possible, returning to the epiglottis and starting new lifting if not successful. We decided to stop the attempt at 120 s or if the patient desaturated to 80%.

We note the Cormack-Lehane glottis visualization at classical laryngoscopy- with values ranging from 1 to 4, the time from classical laryngoscopy until the airway was secured in seconds, the lowest oxygen saturation during the procedure and any other complications occurring during procedure. we document every patient data regarding airway, ENT pathology and difficult airway history. We recorded images to document the challenging cases and prove the efficiency of the RTL. We also took notice of any complications that may have arisen during or after the procedure.

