### **Inclusion criteria**

The study will include adult patients with ASA physical status 1–3, requiring surgery for an ENT pathology and having a presumed difficult airway which will be divided in two groups: anatomically difficult airway group according to The Simplified Airway Risk Index Scale(SARI), with a SARI score  $\geq 5$ , and patients with obstructing airway pathology: oropharyngeal tumors, cervical masses, previous neck surgery or radiotherapy, also with predicted difficult intubation forming group 2.

The two groups are needed because ENT pathology is generating a particular challenge in airway approach which is different from the rest of the pathology and the main goal is to show the efficiency of Rigid Tube for Laryngoscopy (RTL) versus gold standard in intubating patients with various types of airway issues. We decided to include at least ten patients in each group, a reasonable number for testing a new method of airway control. Signed informed consent was obtained from all patients explaining the procedure in simple words and detailing the risks and the safety measures.

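### The RTL always follows a conventional laryngoscopy that was not grade 1, so the stated comparison with the gold standard cannot be read as a device effect

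*Combined protocol and SAP*

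**What the plan says.** **Goal.** Under *Inclusion criteria*: "the main goal is to show the efficiency of Rigid Tube for Laryngoscopy (RTL) versus gold standard in intubating patients". The two groups defined there are patient types (anatomical difficulty, obstructing pathology), not device arms, with at least ten patients in each.

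**Order.** No single sentence fixes it, but three things under *Exclusion criteria* do:
- After induction and one minute of mask ventilation, "classical laryngoscopy was performed with a McIntosh curved blade laryngoscope" and the Cormack-Lehane grade is registered. The RTL technique is described after that: "The RTL intubation starts with the head in extension and in sniffing position, using a retromolar approach, with teeth protection".
- The investigators will "reject from the study patients who exhibit a Cormack-Lehane grade 1 glottis view when conventional laryngoscopy is performed", which requires the conventional look to come first.
- The recorded time is "the time from classical laryngoscopy until the airway was secured in seconds", so the clock starts at the conventional look.

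**Exception.** If mask ventilation is difficult with marked desaturation, "we will take the first chance to secure the airway considering potentially unsafe the use of the experimental RTL". Such patients may contribute no RTL data.

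**Analysis.** The *Statistical analysis plan* is descriptive: mean and SD of time for conventional laryngoscopy and for RTL intubation, median and range of grade, mean and SD of lowest saturation, and complications. It has no test, no term for order and no limit on interpretation.

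**The concern.** A goal worded as one technique against another needs data in which the techniques differ by something other than their place in the sequence. Here the operator has already seen the airway with the blade when the RTL is introduced, more time has passed since induction, and the first look may have affected oxygen reserve and tissues. Prior sight of the airway could help the RTL; the other factors could count against it.

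Selection is a second problem. The first look decides who stays, so grade 1 is removed from the conventional results but not from anything observed later.

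At stake is the conclusion. A reader who sees two mean times side by side, under a goal of RTL versus gold standard, will take the difference as the effect of the device.

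**Working it through.** The plan gives no power, effect size or other calculated figure on this point, so there is nothing to reproduce.

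**1. Can device be separated from order?** Take the planned minimum, 2 × 10 = 20 patients, each with a conventional and an RTL value. The parameters are 20 patient effects + 1 device + 1 order = 22.

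| Sequence | Rank | Parameters |
|---|---|---|
| Conventional then RTL in all 20 | 21 | 22 |
| Balanced 10/10 (for contrast only) | 22 | 22 |

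In the fixed sequence the device column and the order column are identical, at any sample size. Patients who never reach the RTL add no RTL value and do not break this.

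**2. Which outcomes have a value for each technique?**

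| Outcome | Procedure text | Statistical analysis plan |
|---|---|---|
| Time | One interval, from conventional look to secured airway | A time for each technique |
| View | Grade at classical laryngoscopy only | Grade, technique not named |
| Saturation | One lowest value (a further reading precedes the first look) | Lowest value |
| Complications | During or after the procedure | During and after the procedure |

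Only time is clearly set side by side, so the aliasing applies there directly. Saturation and complications cannot be assigned to either device.

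**3. What would the grade 1 rejection do if an RTL view were graded?** The documents give no grade mix or misgrading rate, so both are assumed. Suppose two equally good, independent looks at the same true grade (1 to 4; the intermediate value 3.5 is left out), each wrong by one step with probability e in each possible direction. Keep patients whose first look is grade 2 or worse. Because the two looks are exchangeable, moves among grades 2 to 4 cancel, and

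net share looking better = P(first ≥ 2, second = 1) / P(first ≥ 2).

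Example, true mix 30/35/25/10%, e = 0.10:
- Numerator: true grade 1, 0.30 × 0.10 × 0.90 = 0.0270. True grade 2, 0.35 × (0.80 + 0.10) × 0.10 = 0.0315. Sum 0.0585.
- Denominator: 1 − (0.30 × 0.90 + 0.35 × 0.10) = 0.695.
- Net: 0.0585 / 0.695 = 0.084.

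| True mix, grades 1–4 | e | Better | Worse | Net |
|---|---|---|---|---|
| 30/35/25/10% | 0.05 | 10.7% | 6.3% | 4.4 points |
| | 0.10 | 19.9% | 11.4% | 8.4 points |
| | 0.15 | 27.5% | 15.5% | 12.0 points |
| 10/35/35/20% | 0.05 | 8.9% | 6.5% | 2.4 points |
| | 0.10 | 16.7% | 12.1% | 4.6 points |
| | 0.15 | 23.3% | 16.7% | 6.7 points |

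Net values are taken before rounding. Among 20 retained patients the range is 20 × 0.024 ≈ 0.5 to 20 × 0.120 = 2.4 patients. The median grade is 3 at both looks in all six rows; the range does change, because grade 1 can reappear.

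**4. A second model.** With bivariate-normal looks, 10% to 40% grade 1 at any single look, correlation 0.5 to 0.8 and no device effect, the second look shows about 5% to 27% grade 1. The first shows 0% by construction.

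**The case against.** The strongest reply is that this is a small descriptive feasibility series. The plan contains no test, paired difference or superiority criterion, and the order cannot be otherwise because eligibility depends on the first look. Most outcomes have no separate value per technique, and the conventional step is described only as a look and grading, with no intubation attempt, so the tasks differ as well. On this view order is secondary to the lack of a clear comparator outcome.

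Much of that stands:
- A reader might infer that view, saturation and injury will all be compared between devices. The documents do not support this; only the two times are clearly tabulated together.
- A reader might infer that the fixed order favours the RTL throughout. It does not follow. A directional bias can be shown only for grade, and only if an RTL grade is taken.
- Quoting 20% better at the second look would overstate the selection effect. With the 30% mix and 10% misgrading, 13.8% move each way with no selection at all. The net figure is the relevant one, the 30% grade 1 share may be high for patients chosen for a predicted difficult airway, and the planned median does not move.

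The reply does not remove the point. The goal is still worded as a comparison, the two times still appear together, and nothing in the plan tells the reader that their difference is not a device effect. The need for the order explains the design but does not identify a device effect. The difference in task makes the comparative wording harder to defend, not easier.

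**Conclusion.** The point holds with limited scope. The goal claims more than the design can deliver. For patients who reach the RTL, device and order are wholly aliased, which rests on the order inferred from the narrative, the grade 1 rejection and the time clock. The effect on the two times has unknown size and sign. If an RTL grade is recorded, selection favours the RTL by a net 2 to 12 points under the assumptions shown; the size depends on those assumptions.

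It would go too far to say that the series is uninformative, that the order should have been randomised, or that the plan announces a superiority analysis. The data can describe how the RTL performs after a conventional look that was not grade 1. They cannot describe it as a first technique or show that it is better than the blade. This should be corrected, but it does not call for a change in conduct.

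**What to change.** Keep the order.

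- *Inclusion criteria*, goal sentence: replace the comparison with a description, for example: *to describe the performance of the RTL as a second technique, in patients whose preceding conventional laryngoscopy was not grade 1.*
- *Statistical analysis plan*, add: *RTL results are reported in absolute terms. Lowest saturation and complications are reported for the combined sequence of conventional laryngoscopy and RTL. No statement of superiority over, or replacement of, conventional laryngoscopy will be made.*

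This is a change of wording only; recruitment, procedure and recorded data stay as they are. The cost is a narrower claim.

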### **Statistical analysis plan**

The statistical part will consist of creating a table with the pre-anaesthetic and demographic variables – mean and standard deviation. The results will be included in a table and graphic image and the data which will be analysed are:

- time for conventional laryngoscopy and for intubation with the RTL- mean and SD
- grade of glottis view as from Cormack-Lehane scale- median and full range

- haemoglobin oxygen saturation during the procedure with the lowest noted as mean and SD
- complications during and after the procedure

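### Whether the RTL achieved intubation is not a named outcome, and the planned mean RTL time cannot show how often it did

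*Combined protocol and SAP*

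**What the plan says.** The Inclusion criteria section gives the main goal as showing the efficiency of the RTL against the gold standard in intubating patients, with at least ten patients in each of two groups.

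The RTL procedure, printed under Exclusion criteria, sets limits on an attempt: "We decided to stop the attempt at 120 s or if the patient desaturated to 80" (percent saturation). It also foresees a further try: "A second attempt will be started advancing slower".

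The same section lists what is recorded:

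- glottic view: "We note the Cormack-Lehane glottis visualization at classical laryngoscopy"
- a time: "the time from classical laryngoscopy until the airway was secured in seconds"
- the lowest saturation and any complications
- general airway data: "we document every patient data regarding airway, ENT pathology and difficult airway history"

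It adds: "We recorded images to document the challenging cases and prove the efficiency of the RTL".

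The Statistical analysis plan lists four outputs:

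- "time for conventional laryngoscopy and for intubation with the RTL- mean and SD"
- Cormack-Lehane grade, as median and range
- lowest saturation, as mean and SD
- "complications during and after the procedure"

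Neither list names RTL intubation success, or the number of attempts started, stopped or completed.

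**The concern.** For a device meant to intubate difficult airways, the first result a reader wants is the number of patients it intubated out of those in whom it was tried. The protocol accepts that some attempts will be stopped, but it does not ask for that count. The plan could be followed to the letter without ever reporting it.

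The time summary adds to the problem. A stopped attempt is not an intubation with the RTL, so on the literal reading it contributes no time. The patients in whom the device failed drop out of the mean, and the RTL can look faster than it is. The sentence that speaks of proving efficiency relies on images of challenging cases, which are a selected set and not a count over all attempted patients.

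**Working it through.** The plan contains no success rate, expected time or sample-size calculation, so there is no figure to reproduce. The check is whether any listed output would reveal RTL success, followed by illustrations. Only the 120 s and 80% limits and the minimum of ten per group come from the documents. All patient values below are assumed.

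**Can the listed outputs supply the count?**

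- *Time, as worded in the SAP.* It exists only where the RTL intubation was completed. No x of n is requested.
- *Time, as recorded in the procedure text.* It starts at classical laryngoscopy, ends when the airway is secured and names no device. It would include rescue by other means, unmarked.
- *Cormack-Lehane grade.* It is taken at classical laryngoscopy, so it cannot show what the RTL then achieved.
- *Lowest saturation.* Stops at 80% cannot be counted from a mean and SD, and a stop at 120 s need not lower saturation at all.
- *Complications and general airway data.* A failed RTL intubation could be entered under either, but neither text says so.

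**(a) Same printed time, different success.** Ten patients each.

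- Set A, 10 of 10 intubated: 45, 48, 54, 60, 60, 60, 60, 66, 72, 75 s. Mean 60.0; sum of squared deviations 810; SD = √(810/9) = 9.49.
- Set B, 5 of 10 intubated and five stopped at 120 s: 48, 54, 60, 66, 72 s. Mean 60.0; sum of squared deviations 360; SD = √(360/4) = 9.49.

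Both print 60 (9.5) s. Success with exact (Clopper-Pearson) 95% CI is 100% (69.2–100%) for A and 50% (18.7–81.3%) for B.

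**(b) Dependence on the time definition.** Eight successes with mean 60 s, two patients stopped at 120 s.

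| Reading | Calculation | Mean |
|---|---|---|
| Successes only | 8×60/8 | 60 s |
| Stop time entered | (8×60 + 2×120)/10 | 72 s |
| Airway secured by rescue at 180 s | (8×60 + 2×180)/10 | 84 s |
| Airway secured by rescue at 240 s | (8×60 + 2×240)/10 | 96 s |

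**(c) Saturation.** Lowest value 96% in eight patients and 80% in two stopped patients: mean (8×96 + 2×80)/10 = 92.8; SD = √[(8×3.2² + 2×12.8²)/9] = √(409.6/9) = 6.75. The printed summary does not show that two attempts were stopped.

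**(d) Scope of the 120 s limit.** Suppose seven patients are intubated at the first attempt, one is stopped at 120 s and then intubated by RTL at a second attempt, and two are never intubated by RTL. Success is 8/10 (44.4–97.5%) if the limit is per attempt and 7/10 (34.8–93.3%) if it is total.

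**(e) Would failures be expected?** With assumed true failure rates of 5%, 10% and 20%, the chance of at least one failure in n patients is 1 − (1 − p)ⁿ. This gives 40%, 65% and 89% for n = 10, and 64%, 88% and 99% for n = 20.

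**The case against.** The strongest objection is that the successes-only reading may not be the intended one. Only one time is recorded, and it runs until the airway is secured. If the SAP uses that variable, failures stay in with their rescue time and the RTL looks slower, not faster. That is right as far as it goes: the direction of the distortion depends on a definition the documents leave open. It does not rescue the plan, because on that reading too the mean says nothing about how many patients the RTL intubated.

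Three further points have some force:

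- The recorded-data sentence sets the lowest saturation beside other complications, which suggests that desaturation may itself be reported as one. A stop at 80% might then be visible, but a stop at 120 s would not.
- A table that happened to print n next to the mean would expose the gap in illustration (a). The plan does not require this. The two data sets were chosen to share a mean and SD, so they show what is possible and are not an estimate.
- The second attempt is described before the stopping rule, and nothing says it follows a stop. Example (d) therefore rests on an assumed sequence, and it shows only that the coding rule must be settled.

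It can also be said that a descriptive study of about 20 patients needs nothing beyond x of n. That count is indeed the core of the repair, but a time summary that drops failures or mixes them with rescue would still mislead beside it.

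**Conclusion.** The concern holds and should be fixed before analysis. Across the sections from Inclusion criteria to the Statistical analysis plan, stopped attempts are foreseen, RTL success is not named, and the planned mean time is either conditional on success or mixed with rescue. Times, saturation and complications do bear on efficiency, but they can look the same for a device that usually works and one that often fails.

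The size cannot be determined from the documents. The effect on the time summary is zero if no attempt is stopped; even then, 10 of 10 would be the key result and the plan does not ask for it. Under the assumed values, one printed time is compatible with 100% and with 50% success, and two failures in ten move the mean from 60 s to between 72 and 96 s, depending on the definition. The absence of a named success outcome depends on none of these assumptions.

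**What to change.** 1. **Reconcile the definitions first.** State which time the SAP analyses, with its start, its end and the device that secures the airway. State whether the 120 s limit applies per attempt or in total. Code any patient stopped once and then intubated by RTL according to that rule. The clinical limits themselves are not changed.
2. **Add the outcome to the SAP.** Per patient, *intubated by RTL within the protocol's limits*, reported as x of n by group and overall with an exact 95% CI, over all patients in whom the RTL was started. Count separately those in whom it was withheld because of difficult mask ventilation with marked desaturation, as the Exclusion criteria section allows.
3. **Summarise RTL time over all attempted patients.** Use the cumulative proportion intubated by RTL, or a median where fewer than half fail. Keep patients never intubated by RTL as not intubated; do not censor them at the stop time. Give a mean and SD only if labelled *successes only*, with x of n.

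The cost is SAP wording and one yes/no field per patient, with the reason if not intubated by RTL. Parts of the protocol are in the past tense, so for patients already treated the field must come from the record or be reported as unknown.

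The downsides are that reported times may look less favourable, a median is undefined if half or more fail, and intervals will be wide: 8/10 gives 44.4–97.5% and 16/20 gives 56.3–94.3%. The proportion describes RTL performance and does not by itself supply the comparison with the gold standard.

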### **Statistical analysis plan**

The statistical part will consist of creating a table with the pre-anaesthetic and demographic variables – mean and standard deviation. The results will be included in a table and graphic image and the data which will be analysed are:

- time for conventional laryngoscopy and for intubation with the RTL- mean and SD
- grade of glottis view as from Cormack-Lehane scale- median and full range

- haemoglobin oxygen saturation during the procedure with the lowest noted as mean and SD
- complications during and after the procedure

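### The aim is to show RTL efficiency against the gold standard, but the analysis plan names no deciding outcome or group and does not count whether the RTL secured the airway

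*Combined protocol and SAP*

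**What the plan says.** The aim is in the Inclusion criteria section: "the main goal is to show the efficiency of Rigid Tube for Laryngoscopy (RTL) versus gold standard in intubating patients with various types of airway" problems. Patients are described as "having a presumed difficult airway which will be divided in two groups": one with an anatomically difficult airway, one with obstructing airway pathology. The size is set by judgement: "We decided to include at least ten patients in each group, a reasonable number for testing a new method of airway control".

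The Statistical analysis plan is short. After a table of pre-anaesthetic and demographic variables, it says "The results will be included in a table and graphic image and the data which will be analysed are" and lists four items:

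- "time for conventional laryngoscopy and for intubation with the RTL- mean and SD"
- "grade of glottis view as from Cormack-Lehane scale- median and full range"
- lowest oxygen saturation, as mean and SD
- complications during and after the procedure, with no summary measure

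The procedure text, printed under Exclusion criteria, says an RTL attempt is stopped at 120 s or at a saturation of 80%, and it allows a second attempt. It records the glottic view at classical laryngoscopy, the time from classical laryngoscopy until the airway is secured, the lowest saturation and complications. It also says: "We recorded images to document the challenging cases and prove the efficiency of the RTL".

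**The concern.** A purely descriptive analysis suits a descriptive aim. Here the aim is a claim of efficiency against a comparator, and nothing connects the four summaries to that claim. The plan does not define efficiency, say whether it is judged in group 1, in group 2, in both or in a pool, or say what result would count against the RTL.

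The most direct reading of efficiency in intubation is whether the device got the tube in, and that is not among the items to be analysed. The procedure sets limits at which an attempt is abandoned, so failures are foreseen. A report could follow the plan to the letter, give a short mean time and an acceptable mean saturation, and never state how many RTL attempts failed. It could also let a good result in one group stand for both, although the protocol justifies having two groups on the ground that ENT pathology poses a different airway challenge.

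**Working it through.** The plan gives no figure to reproduce: no alpha, power, effect size, margin or hypothesis test. The check is therefore to take each listed item and ask what it can say about the RTL as the text stands.

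| Item in the Statistical analysis plan | How the procedure text records it | Listed for both techniques? | Shows whether the RTL succeeded? |
|---|---|---|---|
| Time | One interval, from classical laryngoscopy until the airway is secured | Yes | No |
| Cormack-Lehane grade | At classical laryngoscopy only | No | No |
| Lowest saturation | One value for the whole procedure | No | No |
| Complications | During and after the procedure | No | Not as defined |

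1. **Glottic grade.** It is taken before the RTL is used, and grade 1 is an exclusion criterion. As described, it characterises the patients' airways and not the device.
2. **Saturation.** The single lowest value belongs to a procedure that includes the conventional laryngoscopy. No separate value for each technique is described.
3. **Time.** This is the only item with a stated contrast. The recorded interval ends when the airway is secured, without saying by which device. If f of n RTL attempts are stopped, the plan does not say whether those f patients are left out, entered at the stopping time or entered at the time of rescue. If they are left out, the mean over the remaining n − f patients carries no information about f.
4. **Groups.** There are two, neither is named as deciding, and there is no rule on separate or pooled reading.

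So none of the four items is designated as deciding, one is listed for both techniques, and none counts RTL failures.

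**What a success proportion could deliver.** Take the planned minimum of n = 10 per group and, for illustration, assume all 10 have the RTL attempted. The exact (Clopper-Pearson) 95% limits for x successes are the 0.025 quantile of Beta(x, n − x + 1) and the 0.975 quantile of Beta(x + 1, n − x).

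- x = 10: the lower limit is 0.025^(1/10) = 0.692, so the interval is 69% to 100%.
- x = 8: Beta(8, 3) and Beta(9, 2) give 0.444 and 0.975, so the interval is 44% to 97%.

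The values of x are assumptions; the documents give no expected success rate.

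**The case against.** The strongest reply is that the plan is openly descriptive. All four items are listed in advance and promised in a table and a graphic, so an unfavourable one would be visible. That stands for the listed items: the gap there is the missing ranking, not concealment. It does not help with RTL success, which is not listed at all.

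Three stronger readings are tempting, and the documents do not support them.

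- **Inflated false-positive rate.** A reader might count 4 outcomes × 2 groups = 8 chances and, assuming 5% tests, compute 1 − 0.95^8 = 0.34. The plan has no alpha and no test. Glottic grade as recorded cannot favour the RTL, and only time is listed for both techniques. The eight are not eight comparisons, and the figure does not measure selective emphasis.
- **A second confirmatory aim.** The wording about proving efficiency concerns images of challenging cases, not the analysis. The comparative aim rests on the Inclusion criteria sentence alone.
- **No primary outcome exists anywhere.** One part of the document was removed before review, so the absence is established only for the text available.

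It can also be said that a success proportion does not answer a question posed against the gold standard. That is correct: it has no comparator. For that reason the aim must change along with the outcome.

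**Conclusion.** The concern holds in this form: a comparative efficiency aim is paired with unranked descriptive summaries, no item or group decides the question, and RTL success is left out although the procedure foresees stopped attempts. The consequence is that the claim could rest on selective emphasis of time or saturation with failures uncounted. Its size cannot be put as an error rate or a bias, because the plan supplies neither a test nor an expected success rate. The data remain usable and the remedy is nearly free, so this should be corrected but does not invalidate the study. The conclusion assumes that the removed part of the document does not define a deciding outcome and that the procedure text is complete on when glottic grade is recorded.

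**What to change.** In the Statistical analysis plan:

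- Name as the main outcome the proportion of patients whose airway was secured with the RTL without the attempt being stopped under the limits already in the procedure text. State how the outcome treats a second attempt, since the text does not say whether the time limit runs per attempt or overall.
- Put every patient in whom the RTL was attempted in the denominator. Report separately how many patients did not have it attempted, with the reason under Exclusion criteria.
- Report the outcome separately for group 1 and group 2, with exact 95% confidence intervals.
- Label time, glottic grade, lowest saturation, complications and any pooled result as descriptive, and report them in full whatever their direction.

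In the Inclusion criteria section, reword the aim to describing RTL success in each group, because this outcome has no comparator. Do not generalise across airway types from one group alone.

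Much of the protocol is in the past tense. If data were already collected, date the choice of main outcome and disclose that it was made after data collection.

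The cost is a few sentences, with no added patients or procedures, provided that the study records show for each patient whether the RTL secured the airway. The downsides are that a good time or saturation result alone can no longer be presented as showing efficiency, and that intervals from about ten patients per group will be wide.
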